2.2. Describe how randomization or other treatment assignment will be made. **Once inclusion/exclusion criteria are met, we will use a random number table that will be generated using the PROC PLAN macro in SAS v9.3 to randomly assign equal numbers of CGs to the individual TEP + individual care management, group TEP + individual care management, or UC arms. The randomization program will take into account stratification by relationship type (spouse/partner, adult child/other family). This will yield 135 CGs per arm (90 spouses/partners, 45 adult children/other family). We will enroll more spousal CGs than adult children/other family CGs because this distribution more closely reflects the demographic composition of CGs providing care for Veterans with dementia found in our preliminary work.**

2.3. For retrospective research studies, provide the "look-back" period. (e.g., December 1, 1999 through December 31, 2008.) **This is primarily a prospective study. However, for the medical chart review component of the project, data from**

Veterans' medical charts will be extracted for a period of one year prior to the CGs' 3 month research assessment date.

3. Study Duration

- 3.1. Provide the estimated length of time to enroll all subjects and complete the study. **4 years**
- 3.2. Explain the expected duration of subject participation including any follow-up. **Research assessments will be conducted at baseline and 3, 6, and 12 month followup. If randomized to a treatment arm, CGs will receive up to 3 months of care management services.**
- 3.3. Specify the projected date of completion of the proposed study. **February 2019**

4. Drug Information (If not applicable state, "Not Applicable.") Not Applicable

- 4.1. Specify if the drug or biological agent is:
 - 4.1.1. FDA approved **N/A**
 - 4.1.2. Used for off-label purposes **N/A**
 - 4.1.3. Not yet FDA approved. **N/A**
- 4.2. Include the FDA Investigational New Drug (IND) number for all non-FDA approved and off-label drugs, biological agents or nutritional supplements. If not applicable state, "Not Applicable." **N/A**
- 4.3. Provide all relevant information about the drug **N/A**
- 4.4. Explain any wash-out periods, rescue medications permitted and any type of medications not permitted while enrolled in the study. **N/A**
- 4.5. Describe blinding and un-blinding procedures. **N/A**

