In order to monitor the quality of the individual and group care management/TEP sessions and care managers' fidelity to the model, all individual and group sessions will be audiotaped using a digital recorder. 20% of the sessions will be randomly selected by the PI using a random number generator for fidelity purposes. These digital files will be uploaded onto a shared study folder that will reside on the VISN 4 MIRECC server under password protection and made available only to key personnel at both sites. Audio recordings will be encrypted and password protected and will only be used for supervision purposes.

D. Usual Care Procedures: After the initial baseline research assessment described above, participants randomized to UC will be sent general material about VA and community resources for patients with dementia and their CGs. CGs will receive brochures entitled: Rewards of Caregiving; Caring for the Caregiver; A Checklist for New Caregivers; 5 Tips to Avoid Caregiver Burnout; 50 things Every Caregiver Should Know; Balancing Caregiving, Family, and Work; and, Long Distance Caregiving. With the exception of this material, individuals in this group will receive UC and will be contacted again at 3, 6, and 12 months for follow-up research assessments. CGs in the UC group will be free to seek medical, psychological, social support, and social services that are available through VAMCs or any other non-VA/community source.

- 1.2. Explain if and how the follow-up of subjects will occur. **Follow-up CG research assessments will be conducted at 3, 6, and 12 months post-baseline. CG assessments will be conducted by phone or, if the CG prefers, packets will be mailed to the CG along with stamped, return envelopes. CRs' medical charts will be reviewed for a period of up to one year following the 3-month CG assessment.**
- 1.3. Describe where, how and who will be conducting study procedures. **Randomization group will be assigned by the PI, Research Coordinator, or Biostatistician. Screening, research assessments, and chart reviews will be conducted by the Research Assistants. Care management will be provided by Care Managers. Supervision will be provided by Drs. [name], [name], and [name]. All procedures will be conducted at either the CMCVAMC MIRECC or CHERP or VAWNYHS Center for Integrated Healthcare (except in the case where the CG prefers to have the assessment packets mailed to them).**

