Patients referred to study staff through these mechanisms will receive a letter stating that their provider has identified them as someone who might be appropriate for a new program designed to help Veterans with memory problems and their CGs. Within one week of receiving this letter, Veterans and CGs will be called by the Research Coordinator/research assistant to assess interest in participation. We will call the contact number in the Veteran's medical record. If the Veteran answers, we will describe the study and ask for the name and contact information of the family caregiver. The Veterans' identity will be verified by first asking for their full name and the name of their CMCVAMC primary care physician. After telephone discussion of the information in the consent/HIPAA form, and encouraging the asking of questions/concerns, the CG will be asked if s/he gives consent to be enrolled in the study. The Research Coordinator/RA will be using an IRB approved script as well as a checklist to ensure each element of consent is covered. Interested CGs will be mailed a copy of the verbal informed consent form. Non-Veteran caregivers also will receive a Copy of Notice of Privacy Practices, and acknowledgement of its receipt will be noted. Once the consent is fully executed, the Research Coordinator/research assistant will confirm study eligibility by completing the screening assessment. Veteran/CG dyads will be eligible for enrollment if they meet the inclusion/exclusion criteria outlined above. Once eligibility is established, the CG will be randomized to one of the three study arms.

- 8.2. If using a clinic, be specific about who will identify the potential subject and how that information will be transmitted to the research staff. **As described above, clinical staff from primary care will be asked to refer potentially eligible participants to the Research Coordinator. At the completion of the initial BHL/BTC clinical behavioral health assessment, all patients potentially eligible for the study who also have a dementia diagnosis will be informed of the project and asked if they would be interested in being contacted by a Research Coordinator in order to discuss a study for which they might be eligible in participating. BHL/BTC staff will be asked to document in an electronic database (stored on the shared secure, password-protected MIRECC server that will be made available to both sites) the names and phone numbers of patients who agree to further contact.**

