9.5.1.1. Provide the title(s) of individual(s) **Research Coordinator, Research Assistant**

9.5.1.2. Type of training received to perform this process **CITI and VA Human Subjects Training; PI will train staff on consent procedures**

9.5.2. **Pre-Recruitment Screening** (the use of medical records and other data bases to determine populations and individuals eligible for the study), **As described above, at the completion of the initial BHL/BTC clinical behavioral health assessment, all patients potentially eligible for the study who also have a dementia diagnosis will be informed of the project and asked if they would be interested in being contacted by a Research Coordinator. Second, using data extracted from VINCI, we will prepare a list of Veterans who have had at least one PACT encounter in the past six months and who are currently being prescribed a cholinesterase inhibitor or memantine medication and/or have a diagnosis of dementia in their active problems list. The list will also include each Veteran's respective medical provider. Each provider will receive a list of his or her patient names and will be asked to identify any patients who may be eligible for the project, or for whom the provider believes that CG education and support would be a helpful service. Third, we will use data from the Clinical Case Registry to create a list of patients with a diagnosis of dementia and/or who are currently being prescribed a cholinesterase inhibitor or memantine medication who have also seen a primary care provider in the last 6 months. As with the list from VINCI, we will contact each provider before contacting the patients.**

9.5.3. **Recruitment Process** (the process in which individuals are contacted and first introduced to the study and to the possibility of participating as subjects), **Patients referred to study staff will receive a letter stating that their provider has identified them as someone who might be appropriate for a new program designed to help Veterans with memory problems and their CGs. Within one week of receiving this letter, Veterans and CGs will be called by the Research Coordinator/research assistant to assess interest in participation.**

9.5.4. **Informed Consent Process** (the process by which recruited subjects are fully informed about participating in the study and then formally give their voluntary consent for participating),

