9.5.5. **Screening of Recruited Subjects** (those activities in the protocol in which a final determination of eligibility of prospective subjects is made during the early phases of the study, using laboratory data, inclusion and exclusion criteria, and other person-specific information). **Once the consent is fully executed, the Research Coordinator/Research Assistant will confirm study eligibility by completing the screening assessment. Veteran/CG dyads will be eligible for enrollment if they meet the inclusion/exclusion criteria outlined above. Specific screening assessments include: AD8, Zarit Burden Interview.**

9.5.6. Include the breakdown of each individual's responsibilities:

- 9.5.6.1. Principal Investigator, **Ensure participant privacy and confidentiality; Oversee and ensure quality of all aspects of consent process (including periodic audits); Obtain and document consent when needed**
- 9.5.6.2. Co-Principal Investigator, **Ensure participant privacy and confidentiality; Oversee and ensure quality of all aspects of consent process (including periodic audits)**
- 9.5.6.3. Research Coordinator, **Ensure participant privacy and confidentiality; Oversee and ensure quality of all aspects of consent process (including periodic audits); Obtain and document consent; All other consent-related activities (e.g., screening), as described above**
- 9.5.6.4. Additional research staff by title, **Research Assistant-obtain and document consent, ensure participant privacy/confidentiality; All other consent-related activities (e.g., screening), as described above**

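### The Research Coordinator (who consents and screens) and the PI (who consents when needed) may also assign the arm, and no allocation concealment is described

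*Combined protocol and SAP*

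**What the plan says.** Five places in the combined protocol and SAP bear on this.

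- **N.1.3 (who conducts procedures):** "Randomization group will be assigned by the PI, Research Coordinator, or Biostatistician". The next sentence gives screening, research assessments and chart reviews to the Research Assistants.
- **L.2.2 (randomization):** after eligibility is confirmed, caregivers are allocated equally across the three arms from a "random number table that will be generated using the PROC PLAN macro in SAS v9.3", stratified by relationship type, with 135 per arm. No block size, list holder or release procedure is given.
- **Q.8.1 (recruitment):** after consent, "the Research Coordinator/research assistant will confirm study eligibility by completing the screening assessment". Randomization follows once eligibility is established. Q.9.5.5 gives screening to the same two roles.
- **Q.9.5.1.1 (person obtaining consent):** "Research Coordinator, Research Assistant".
- **Q.9.5.6 (responsibilities):** the Research Coordinator and the Research Assistants each have consent and screening duties. The PI oversees the consent process and is also to "Obtain and document consent when needed".

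**The concern.** Randomization protects the comparison only if the person deciding whether and when a caregiver enters cannot foresee the arm. Here the sequence is generated in advance, and two of the three roles permitted to assign from it also take consent. One of those two also screens. If such a person can see the next entry, a call can be timed, or a borderline eligibility judgement made, with the arm in mind.

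This could affect all three Aim 1 contrasts: group against usual care, individual against usual care, and group against individual. The outcomes are caregiver-reported, and a caregiver's motivation and availability plausibly bear both on those scores and on the engagement measured under Hypothesis 2A.

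**Working it through.** No power or error-rate formula applies. The totals agree (3 × 135 = 405) but do not bear on the point. The check is a comparison of the stated roles, followed by a search for safeguards.

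**Step 1. Duties by role.**

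| Role | Consent | Eligibility screen | Assigns arm (N.1.3) |
|---|---|---|---|
| Research Coordinator | Yes (Q.8.1, Q.9.5.1.1, Q.9.5.6.3) | Yes (Q.8.1, Q.9.5.5, Q.9.5.6.3), though not named for it in N.1.3 | Yes |
| PI | When needed (Q.9.5.6.1), though not listed in Q.9.5.1.1 | No duty stated | Yes |
| Research Assistant | Yes (Q.8.1, Q.9.5.1.1, Q.9.5.6.4) | Yes (N.1.3, Q.8.1, Q.9.5.5, Q.9.5.6.4) | No |
| Biostatistician | No duty stated | No duty stated | Yes |

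The Coordinator may do all three for the same caregiver. The PI may do two.

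**Step 2. Does the overlap depend on which screening passage governs?** No. If N.1.3 governs and only Research Assistants screen, the Coordinator still makes recruitment calls, takes consent and may assign.

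**Step 3. Is a safeguard described?** There is no mention of sealed envelopes, central or web allocation, a restricted list, an independent list holder, or release only after eligibility is locked. Four items come close, but none supplies concealment:

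- N.1.1.B says Research Assistants do not know the arm at research assessments. That is assessor blinding, and it does not cover the Coordinator or the PI.
- The timeline in N.2.2 includes building a randomization database, with no access rule.
- REDCap is named for data entry, not for allocation.
- Q.8.1 orders the steps as consent, screen, randomize. That order does not help if the person screening can already see the next entry.

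**Step 4. Is there room to act on foreknowledge?** Some. Several criteria in Q.2.1.1 have fixed thresholds: a 4-item Zarit score of 3 or more, an AD8 score of 2 or more, and co-residence or an average of at least 4 hours of care a day. The exclusion in Q.2.1.2 for caregiver impairment that makes consent, assessment or participation difficult needs staff judgement. Staff also have some control over when calls are made. The group arm needs 5 to 8 caregivers on one call at a set time (N.1.1.C), so there is an ordinary, well-meant reason to prefer available caregivers for it.

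**Step 5. Could the analysis undo it?** Only in part. V.4.2 adjusts for the baseline score and for covariates found imbalanced. Motivation and availability are not among the assessments listed in N.1.1.B, so selection on them would remain. In addition, the baseline assessment follows randomization (N.1.1.B), and a caregiver counts as enrolled only after it (Q.9.7). Loss between assignment and baseline by someone whose arm staff know is a related route to the same problem.

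**The case against.** The strongest reply is that the documents do not show an open list in a recruiter's hands. L.2.2 speaks of a randomization program, and the timeline in N.2.2 lists a randomization database. Assignment is placed after consent and eligibility, the Biostatistician is one of the permitted assigners, and N.1.3 read alone separates screening from assignment. Most screening criteria are numeric.

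Much of this stands as a limit on the claim. A reader might infer four stronger things that the text does not support:

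- **That allocation is known to be unconcealed, or that recruiters see every coming assignment.** The documents are silent on who can view the table. They show only that recruiters may assign and that no concealment is described.
- **That the PI screens caregivers.** No section gives the PI that duty, and the PI's consent role is occasional.
- **That everyone who recruits is affected.** Research Assistants consent and screen but are not named to assign.
- **That the contrasts will be biased, by an amount that can be set against the 0.4 effect size in V.4.1.** Bias is possible rather than certain, and no figure in the documents supports any particular shift.

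The reply does not remove the role rule. N.1.3 expressly permits a person who consents and screens to assign, and nothing elsewhere limits what that person can see.

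**Conclusion.** The concern holds as a permitted role overlap without a described safeguard. It is more than missing detail, because N.1.3 affirmatively names two consent-taking roles as assigners. The consequence is a possible selection bias in the arm contrasts. Its size and direction cannot be estimated from the documents, and adjustment for measured covariates would only partly address it.

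The conclusion rests on two assumptions: that whoever assigns from the table can see at least the next entry, and that no separate procedure outside these documents restricts access. If such a procedure exists, the remedy is to write it in. The change should be made, because the problem cannot be fully repaired after enrolment and prevention is cheap.

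**What to change.** Amend N.1.3, and add a matching sentence to L.2.2, so that:

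1. Only someone with no recruitment role holds the table, either the Biostatistician already named or a restricted-access central system.
2. One assignment is released at a time, after consent and eligibility have been recorded for that caregiver.
3. The PI, Research Coordinator and Research Assistants have no access to the table.

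In the same edit, reconcile N.1.3, which gives screening to the Research Assistants, with Q.8.1, Q.9.5.5 and Q.9.5.6.3, which also give it to the Coordinator.

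The cost is protocol wording and a short delay per participant while the assignment is requested and returned. With the Biostatistician as holder, no new staff are needed.

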2.3. Chart/Records/Data Review (retrospective and/or prospective)

2.3.1. Provide the planned or approximate number of charts/records/data to be accessed

2.3.1.1. CMCVAMC **Charts of 235 Veterans**

2.3.1.2. Other site **Charts of 170 Veterans**

2.3.2. Does this protocol employ an Honest Broker? YES NO

2.3.2.1. If yes, provide name of individual.

2.3.2.2. If no, explain who will access the charts/records.

2.3.2.3. Describe from what database charts/records/data will be accessed.

3. Future Use of Data and Re-Contact, if applicable.

3.1. If any of the participant's data are going to be retained after the study for future research, the following information must be provided to the participant:

3.1.1. Where will the data be stored? **N/A**

3.1.2. Who will have access to the data? **N/A**

3.2. If the subject is going to be re-contacted in the future about participating in future research, this must be specified. Describe the circumstances under which the participant would be re-contacted whether within the VA or outside the VA. **N/A**

3.2.1. If subjects will receive aggregate study results at the end of the study, the informed consent document must contain this information.

4. **Specimen Collection**

4.1. Give the source of all specimens and whether they were collected for research, treatment or diagnosis. **N/A**

4.2. State where specimens will be stored, secured and when discarded. **N/A**

4.3. Explain how destruction of samples will be substantiated. **N/A**

O. **Genetic Testing, if applicable**

1. Explain if the study is looking for an association between a genetic marker and a specific disease or condition, but at this point it is not clear if the genetic marker has predictive value.

Not Applicable

1.1. The uncertainty regarding the predictive value of the genetic marker is such that studies in this category will not involve participant counseling.

1.2. Describe if the study is based on the premise that a link between a genetic marker and a specific disease or condition is such that the marker is clinically useful in predicting the development of that specific disease or condition.

1.3. Will the subject be notified of the results and the provision for genetic counseling?
 Yes No N/A
 1.3.1. If yes, explain further.

1.4. If biological specimens are used in this protocol, please respond to the following questions by checking the appropriate box:

	YES	NO	N/A
a. Does the project involve genetic testing?			
b. Will specimens be kept for future, unspecified use?			
c. Will samples be made anonymous to maintain confidentiality? (Instructions: Note: If there is a link, it is not anonymous. Coding is not anonymous.)			
d. Will specimens be destroyed after the project-specific use is completed?			
e. Will specimens be sold in the future?			
f. Will subjects be paid for their specimens now or in the future?			
g. Will subjects be informed of the results of the specimen testing?			
h. Are there any implications for family members based on specimen testing results? (If yes, they may be participants.)			
i. Will subjects be informed of results obtained from their DNA?			

1.5. Will specimens be de-identified? YES NO N/A

1.5.1. If yes, please describe the procedures to be used.

1.5.2. Include at what point in the process the specimens will be de-identified.

1.6. Describe what measures will be taken to minimize the following risks from breaches of confidentiality and privacy resulting from participating in **THIS aspect** of the research project:

1.6.1. physical
 1.6.2. psychological
 1.6.3. financial
 1.6.4. social
 1.6.5. legal harm

P. **Banking of Collected Specimens**

1. Will collected specimens be banked? YES NO N/A

1.1. **IF BANKING SPECIMENS, IT MUST BE AT AN APPROVED VA REPOSITORY.** (For additional information, refer to [VHA Handbook 1200.12, Use of Data and Data Repositories in VHA Research - March 9, 2009](#).)

1.2. If yes, specify the location where specimens will be banked.

1.2.1. If the location is a non-VA site, has the mandatory approval from the Chief Officer of Research and Development (CRADO) been obtained through submission of a tissue banking application ([VA Form 10-0436](#) - Off-site Application for an Off-site Tissue Banking Waiver)? YES NO N/A

1.2.2. If applicable, attach a copy of the VA Form 10-0436

1.3. Explain how destruction of banked samples will be substantiated.

Q. Subject Recruitment (characteristics of the study population)

1. **Provide the planned or targeted enrollment at:**

1.1. CMCVAMC - 235

1.2. Other sites - 170

1.3. Not applicable; chart review or use of previously collected data -

2. **Screening and/or Eligibility Requirements**

2.1. Describe and provide justification for:

